1.1. Principal Investigator Signature Page

This page will be returned to Access Vascular Inc. and a copy retained at the investigational site.

I have read the attached protocol entitled “A Prospective, Randomized, PICC Asymptomatic Thrombosis Study: A Pilot Study” version C, dated 28 April 2021 and agree to abide by all provisions set forth herein.

I agree to comply with the Investigator’s Obligations stipulated in the Clinical Trial Agreement.

[Redacted signatures]

I agree to ensure that the confidential information contained in this document will not be used for any purpose other than the conduct of the described clinical investigation without the prior written consent of Access Vascular Inc.

Name, Title	Signature	Date Signed (DD/MMM/YYYY)

2. Summary of Changes Table

DOCUMENT HISTORY			
Version	Date	Description of Change	Brief Rationale
A	31 Aug 2020	Initial Version	Initial Version
B	26 Oct 2020	
Added 14 day time point throughout the protocol
 
Updated wording of primary endpoint and added additional “other end points”
 
Primary endpoint: “By using ultrasound technology, the site will measure incidence of all early asymptomatic thrombosis inclusive of superficial thrombophlebitis (SVT) and deep venous thrombosis (DVT) at the first follow up visit (7 days post insertion).”
 
Other endpoints:
 
[REDACTED]
 
[REDACTED]
 
[REDACTED]
 
[REDACTED]
 
[REDACTED]
 
[REDACTED]
	
[REDACTED]
 
[REDACTED]

C	28 Apr 2021	
Administrative Changes only:
 
Updated to Version C and date in header and title page.
 
Updated the wording in the protocol signature page.
 
[REDACTED]
 
[REDACTED]
 
[REDACTED]
 
[REDACTED]
 
[REDACTED]
 
[REDACTED]
 
[REDACTED]
 
[REDACTED]
	
[REDACTED]

	 A large rectangular area of the page is completely blacked out, indicating redacted content. The redaction is approximately 275 pixels wide and 220 pixels high, centered in the middle column of the table.	

Exclusion Criteria:	
 1) Is pregnant, lactating, or is planning to become pregnant during the time of the study 2) Has been previously enrolled in this post market clinical evaluation, or is participating in another clinical study that is contraindicative to the treatment or outcomes of this investigation 3) Venous thrombosis in any portion of the vein to be catheterized 4) Conditions that impede venous return from the extremity such as paralysis or lymphedema after mastectomy 5) Orthopedic or neurological conditions affecting the extremity 6) Anticipation or presence of dialysis grafts or other intraluminal devices, including pacemakers, within a month of patient enrollment start 7) Patients who are on anticoagulation therapy prior to the study (10-14 days). Note: (If patients are placed on anticoagulation (low dose) therapy while hospitalized, these patients are allowed.) 8) Patient has relinquished control of care to a guardian and/or facility 9) Patient has any significant medical or physical condition that, in the opinion of the PI, would make the subject unsuitable for participation in the post market clinical evaluation 10) Inability to complete the protocol in the opinion of the clinical staff due to safety or other reasons
Study Duration:	
Enrollment is expected to take about 2 months.
 
Data collection completed when Last Subject Last Visit occurs. (Calculated by date of procedure + 12 days for the last subject)

Reported Adverse Event Data:	Product observations and adverse events will be collected and reviewed per
	[REDACTED] (product complaints). Additional safety evaluations will be
	performed if needed.

Schedule of Activities

Subject Timepoints	Visit 1 Screening (- 7 days)*	Visit 2 Procedure (0 day)	Visit 3 7 day evaluation (± 5 days)	Visit 4 14 day evaluation and End of Study (± 7 days)***	Unscheduled visits (as needed)
ICF	X				
Inc/Ex criteria	X				
Medical History	X				
Demographics	X				
Con Meds	X	X	X	X	X
Labs (specific per protocol and standard of care)	X	X	X	X	X
Randomization	X**	X**			
Surgical Summary		X			
Ultrasound (as needed per DVT, AND at these specific timepoints)			X	X	X
AE/SAEs		X	X	X	X
Follow up form/unscheduled visit form			X	X	X
End of study forms				X	

*Screening can happen on the same day of the procedure. Screening can also happen 7 days prior to the procedure.

**Randomization can occur at screening or prior to procedure.

***Visit 4 to be scheduled at least four days post visit 3 to avoid overlap. The windows are needed to accommodate scheduling.

5. Introduction

5.1. Background

Access Vascular has developed a novel, bulk-hydrophilic catheter material represents a fundamental shift in material technology. Catheters used for vascular access are commonly prepared from polyurethanes or silicones that provide flexibility, durability, and strength (Renner, 1998), (JM, 1995); however, these polymeric materials are hydrophobic and therefore susceptible to non-specific protein adsorption (Jordon SW, 2007), (Tal MG, 2008). Access Vascular has developed a [REDACTED] hydrogel material PICC line used to access the central venous system via a peripheral vein. Hydrogels have found use in many different medical applications due to their high tolerability. As a result of several factors, including a high-water content and neutral surface charge, Access Vascular's material may mask the catheter from the body significantly more effectively than traditional catheters, resulting in a significantly lower rate of thrombosis. [REDACTED]
[REDACTED]
[REDACTED]
[REDACTED]

The study purpose is to perform a preliminary evaluation of the Hydrogel technology to confirm the performance of the catheter, including evaluating thrombosis incidence [REDACTED] by using UltraSound technology in-vivo. The secondary objective of this study is to evaluate the symptomatic thrombosis incidence rate in the two groups by using ultrasound technology. [REDACTED]

5.2. Disease and Medical Condition State

Venous catheters are used to enable intravenous access for delivery of therapeutics such as antibiotics, chemotherapy, or parenteral nutrition, and for other applications such as blood draws. In the US, approximately 500 million procedures involving venous catheters are performed each year (McGee, 2003), (O'Grady, et al., 2011), (Kornbau, Lee, Hughes, & Firstenberg, 2015).

Thrombosis is the formation and accumulation of blood platelets inside a blood vessel. There were many doctors who had theories about thrombosis, but it was through the works of Rudolf Virchow who described 3 factors that contribute to the development of venous thrombosis: hypercoagulability, stasis of blood flow, and endothelial injury (Bagot & Arya, 2008). When the body detects a potential threat to a blood vessel, such as blood vessel injury or a foreign object, one of the body's responses is to trigger the clumping of platelets against the perceived threat, creating blood clots. In most situations, this reaction is vital to the organism's survival, as the clumping prevents further blood loss or neutralizes a threatening foreign object. However, this response can be harmful in the case of venous access, since the body interprets the catheter as a foreign object and triggers clotting against the catheter.

Several factors can contribute to the formation of thrombus, including, but not limited to, patient disease states inducing elevated systemic prothrombotic states (Van Rooden, 2005), peripheral versus central insertion (Fallouh, 2015), catheter tip malposition (Luciani, 2001), ratio of catheter size to vein diameter (O'Brien, 2013), catheter and/or infusate composition (Caroline Berube, 2017). Although symptomatic line-related thrombosis incidence rates for PICCs range between 3-20% (Zochios, 2014), (Abdullah, 2005), the total rate of upper extremity thrombosis related to the insertion of PICC devices is much higher, with one study measuring 38.5% of patients experiencing a UEVT, and some patient populations at higher risk (i.e. cancer) reaching rates as high as 60% (Luciani, 2001). Although asymptomatic, UEVT has been associated with elevated rates of more serious adverse events such as pulmonary embolism and catheter-related sepsis.

There is a lack of research in regards to adult asymptomatic thrombosis (Pinelli & Balsorano, 2019). The current asymptomatic research study is from the pediatric population where they found a high rate of asymptomatic catheter-related thrombosis (22%) in pediatric patients needing central venous catheters (Pinelli & Balsorano, 2019).

[figure not shown]
The terminology also needs to be defined clearly because there is some confusion. In a study conducted by Baskin et al., they referred to asymptomatic thrombosis as “fibrin sheath”. Other terminology used is also “pericatheter thrombosis” and “pericatheter thrombotic apposition” (Pinelli & Balsorano, 2019). We must be clear about the definition for this study. In this protocol, we are looking for asymptomatic thrombosis using ultrasound technology. This specifically means we are looking for PICCs with echogenic mass in or on the lumen, but no limb swelling, tenderness, or any symptomatic issues.

More recently, in 2020, there was a study published on Chinese cancer patients using ultrasound and looking at asymptomatic venous thrombosis. In this study by Wang et. al, they were able to find that the incidences of PICC related upper limb asymptomatic thrombosis was 48.82%, and the median to observe these thrombi was 3 days. Within 24 hour of PICC insertion, there were 37.1% of patients with asymptomatic thrombosis, and within 1 week, that rate jumped to 85.49% (Wang, et al., 2020). They showed that asymptomatic thrombosis can occur at an early stage. Asymptomatic thrombosis is the way for some bodies to adapt to the trauma of PICC insertion. If this can be detected earlier, then patients will be treated appropriately, and veins for future vascular access needs can be saved.

As a result of thrombus related complications, catheter manufacturers have commercialized products focused on addressing these complications. Nearly all venous catheters are made from polyurethane, and several manufacturers, including the market leader, continue to sell standard, undifferentiated polyurethane catheters. Some companies have added anti-microbial coatings to their devices to provide anti-infective ability. Others have incorporated additives which attempt to mask the device from the body. While somewhat effective, these catheters are nonetheless primarily made of polyurethane and silicone. Although little difference exists in complications rates between the two materials (Seckold, 2015), both materials remain susceptible to the thrombus related complications described above.

5.3. Overview of Non-Clinical Studies

5.4. Overview of Clinical Studies

No clinical studies have been conducted with the current HydroPICC.

6. Study Rationale

6.1. Risk/Benefit Assessment

The current products in this study are FDA 510k cleared. The HydroPICC will be referred to as the investigational product for the purposes of this protocol. There are no study risks associated with the use of the HydroPICC or the competitor PICC. The benefit would be to analyze if a new material in this space would have better outcomes for patients who are in need of this type of medical device.

Though rates of symptomatic thrombosis vary from 3-23% (Chin, Zimmerman, & Grant, 2005), rates of asymptomatic venous thrombosis have been reported as much higher at 48% (Wang, et al., 2020). This study will assess the rate and severity of asymptomatic upper extremity venous thrombosis associated with the use of Access Vascular's FDA-cleared HydroPICC as compared to a competitor device.

7. Study Objective (s) and Endpoints

The study purpose is to take a preliminary look at the Hydrogel technology to examine the asymptomatic thrombosis incidents [REDACTED] by using Ultrasound technology in-vivo.

7.1. Primary Objective and Endpoints

The primary purpose is to examine the incidents of early asymptomatic thrombosis between the HydroPICC arm and the comparison arm.

By using ultrasound technology, the site will measure early incidents of all asymptomatic thrombosis inclusive of superficial thrombophlebitis (SVT) and deep venous thrombosis (DVT). Subjects will be requested to have the PICC line scanned at 7 days (\pm 5 days), and at any unscheduled visit where a symptomatic SVT or DVT is suspected.

The ultrasound evaluation will be classified as (1) without thrombosis or (2) with limited (~2-4mm), (3) large (~4 mm), or (4) occlusive thrombosis, as compared to baseline. Please see the ultrasound section below for more details.

7.2. Secondary Objective and Endpoints

The secondary objective of this study is to evaluate the symptomatic thrombosis rate in the two groups by using ultrasound technology.

By using ultrasound technology, the site will measure all subjects to look for incidents of symptomatic thrombosis. Subjects will be requested to have the PICC line scanned at 7 days (\pm 5 days), 14 days (\pm 7 days) and at any unscheduled visit where a DVT is suspected.

The ultrasound evaluation will be classified as (1) without thrombosis or (2) with limited (~2-4mm), (3) large (~4 mm), or (4) occlusive thrombosis, as compared to baseline. Please see the ultrasound section below for more details.

7.3. Other Objectives and Endpoints

8. Study Design

This is a single-site, pilot, nonblinded randomized controlled performance evaluation to compare two brands of commercially-available single lumen PICC lines. This is a postmarket clinical evaluation and not a statistically powered study.

8.1. Study Overview

This post market clinical evaluation is a prospective, randomized post-market assessment. Each eligible subject will receive a single lumen PICC device and will be placed per the manufacturer's IFU and in accordance with institutional policy.

Per institution policy, due to the fact that the HydroPICC is not a standard of care device, the patient will be consented prior to insertion. This consent will follow the institution's standard of care policies.

any patient receiving a single lumen PICC will be approached to join this study. After the patient consents, and the site reviews the inclusion criteria, the subject can be randomized.

Screening data will be reviewed to determine subject eligibility. Subjects who meet all inclusion criteria and none of the exclusion criteria will be entered into the study. There is an exclusion criteria which requires an ultrasound, and a subject can still be screen failed at the time of insertion.

The following treatments will be used:

AVI device: Access Vascular HydroPICC Single Lumen PICC

Comparator device: [REDACTED] Single Lumen PICC

Vein: Preference is Basilic Vein followed by Brachial Vein, then Cephalic Vein

Once a subject is inserted with a PICC line, they are considered enrolled.

Total duration of subject participation will be the duration for which the catheter is indwelling in the patient up to 16 days. The total study duration is expected to not exceed 23 days, including procedural pre-screen. Insertion of the PICCs will be prioritized with the following: Basilic vein then Brachial vein followed by Cephalic vein. Diagnosis of both asymptomatic and symptomatic vein thrombosis will be established by Doppler ultrasound examination. Examinations will be performed prior to device insertion to establish patient baselines.

[figure not shown]
Ultrasound will be performed pre-insertion of the device, at 7 days post-insertion (± 5 days) and 14 days (± 7 days). Data will be collected using a scale defined previously.

9. Study Methods and Measurements

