10.6. Screen Failures

Any subject who signs an informed consent but fails to meet the required entry criteria is considered to be a Screen Failure. Screen Failure subjects will have their demographic information captured in the appropriate CRF with the reason for screen failure specified. No other information will be collected or analyzed. Since this is a pilot study, the analysis will be conducted on 10 subjects on each arm. If a

[figure not shown]
screen failure occurs, the investigator will need to continue to consent, randomize, and enroll until the 10 subjects for each arm is completed. A second set of randomization envelopes will be used for the recruitment of these screen failed subjects.

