10.7. Enrollment

A subject is considered enrolled when the assigned PICC is inserted. Due to the current situation with COVID, the sponsor is concerned about lost to follow up rates. To prepare for this, the site will enroll 4 extra subjects bringing the total to 24. The plan is to analyze 10 enrolled subjects on each arm, but the site will recruit for 12 in case of COVID related follow up issues.

Screening process

A Prospective, Randomized PICC Asymptomatic Thrombosis Study (PROPATH)	Number: 20-002 Version: C 28Apr2021 Page: 17 of 30
---	---

11. Discontinued Subjects

If a subject is unable to complete the study for any reason, then the investigator will use the screen failed randomization envelope to recruit for this discontinued subject. Data from the discontinued subject will not be used for the per protocol analysis. However, demographics will be used for the recruitment analysis. Any subjects in section 12 described below will be replaced using the method mentioned in this paragraph.

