14.2. Surgical Visit- (Visit 2)

1. Perform and record vital signs.
2. Record labs, if available.
3. Conduct Ultrasound prior to insertion of the assigned PICC. Screen fail if necessary.
4. Insert device per assigned randomization, IFU, and institutional procedures.
5. Confirm patient entry into study.
6. Take picture of insertion site.
7. Record adverse events (if any).

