16.1. General Considerations

Study data will be made available in listings or electronic files as needed. The study results will be reported in tabular form using descriptive statistics, confidence intervals, or statistical tests as indicated.

All summaries will be done by randomized treatment group. Numeric descriptive statistics include the n, mean, standard deviation (SD), median, minimum value, and maximum value. These will be calculated for all numeric baseline data. Categorical summaries will show the number and percent of subjects in the levels associated with the variable summarized and the analysis performed. Percentages will be calculated based on the total number of subjects with non-missing data for the assessment. The denominator should be included for each summary to indicate the set of subjects being summarized.

For any inferential analyses, a two-sided p-value of less than or equal to 0.05 will be considered statistically significant. Any confidence intervals provided will be two-sided 95% intervals. The primary effectiveness assessment is considered the primary analysis. This study is not intended to support claims and the other statistical tests included are intended to assist with reporting, hence, no other adjustment for multiplicity will be used.

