16.2. Sample Size Justification

This is a pilot study to see if the ultrasound endpoint is feasible for a larger study. No power analysis was conducted for this study.

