16.4. Accountability and Baseline Data

Study completion information including reasons for discontinuation and visits completion information will be summarized. Baseline demographics, medical history, and BMI (kg/m²) will be summarized descriptively.

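### The device may be assigned before the pre-insertion scan in an unblinded trial, so the vein can be chosen with the device known, and the planned summaries would not show it

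*Combined protocol and SAP*

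**What the plan says.** **Vein.** Section 8.1 states: "Vein: Preference is Basilic Vein followed by Brachial Vein, then Cephalic Vein". The same order appears again later in that section. Neither statement says what would move the operator from one vein to the next.

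**Timing of assignment.** Section 10.5 allows the investigator to assign the device before the baseline ultrasound. Section 14.1 lists randomisation as step 9 of Visit 1. A footnote to the schedule of activities permits it either at screening or before the procedure. The pre-insertion scan is step 3 of Visit 2 (14.2), and step 4 reads "Insert device per assigned randomization, IFU, and institutional procedures". Section 12.2 says there is no blinding.

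**Contributors to thrombus.** Section 5.2 names, among others, "ratio of catheter size to vein diameter" and malposition of the catheter tip.

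**Analysis.** Apart from completion and discontinuation information, section 16.4 plans to summarise "Baseline demographics, medical history, and BMI". Section 16.5.1 uses a Cochran-Armitage trend test and Fisher's exact test, with no covariate or stratum named. The schedule lists a Surgical Summary at Visit 2 without describing its contents.

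**Scale.** Section 10.6 says "the analysis will be conducted on 10 subjects on each arm", and section 16.2 says "No power analysis was conducted for this study".

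**The concern.** Randomisation balances, on average, whatever is fixed before assignment, such as the patient's vein anatomy. It gives no such protection to a decision taken afterwards by someone who knows the assignment.

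Here that decision is which vein to use. The route to the outcome is short: device known, vein chosen, vein diameter, catheter-to-vein ratio, thrombosis. If the operator moves down the order of preference more readily for one device than for the other, knowingly or not, the arms will differ for a reason that is neither chance nor catheter material. The planned summaries would leave no trace of it.

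What is at stake is the reading of the observed difference between arms and its use in planning the larger study for which section 16.2 says this pilot prepares.

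**Working it through.** **1. The plan's own figure.** Section 10.6 gives 10 analysed per arm, and section 10.7 says "To prepare for this, the site will enroll 4 extra subjects bringing the total to 24". The arithmetic agrees: 2 × 10 + 4 = 24 = 2 × 12. There is no power or effect size to reproduce.

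**2. Sequence of steps.**
- Visit 1, step 9 (14.1): randomise.
- Visit 2, step 3 (14.2): ultrasound, with the PICC already assigned.
- Visit 2, step 4: insert the assigned device.

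Followed as written, this order means the device is known when the veins are first scanned for the study. The schedule footnote also permits assignment shortly before the procedure, so a different order is already compatible with the plan. It is simply not required.

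**3. Size of the bias, illustrative only.** Suppose the device has no effect. Let r0 be the thrombosis risk with a lower-risk insertion, r1 the risk with a higher-risk insertion, and qA and qB the shares of higher-risk insertions in the two arms. Then

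spurious difference = (r1 − r0) × (qB − qA).

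None of these four inputs is in the documents; all are assumed.
- Smallest case: r0 = 0.40, r1 = 0.60, shares 0.20 and 0.30. Difference = 0.20 × 0.10 = 0.02.
- Largest case: r0 = 0.30, r1 = 0.90, shares 0.10 and 0.50. Difference = 0.60 × 0.40 = 0.24.

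Over the 16 combinations tried, the spurious difference runs from 2 to 24 points.

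**4. Comparison with the trial's precision.** The criterion in section 16.1 is that "a two-sided p-value of less than or equal to 0.05 will be considered statistically significant". Enumerating Fisher's two-sided test at 10 per arm:
- Significance needs, for example, 5/10 v 0/10 or 8/10 v 2/10, a gap of 50 to 60 points.
- The probability of p ≤ 0.05 is about 0.013 when the arms have equal risk. Across the scenarios in step 3 it is 0.013 to 0.076.
- With 48% in both arms (the background rate cited in 6.1, not a planning assumption), the approximate 95% half-width is 1.96 × √(2 × 0.48 × 0.52 / 10) = 0.438, or 44 points.

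**5. Chance imbalance, kept separate.** For a binary insertion factor with prevalence q, and two independent Binomial(10, q) counts, the probability that the arms differ by 3 or more subjects is 0.06, 0.16, 0.22, 0.25 and 0.26 at q = 10%, 20%, 30%, 40% and 50% (assumed values). This is what proper randomisation produces at this size. It does not measure the defect.

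**The case against.** The strongest reply is that this is an unpowered pilot which section 16.1 says is not meant to support claims, and that nothing in the documents suggests operators would choose veins by device. The order of preference also limits discretion, though it does not remove it. Even a generous bias is small beside a 44-point half-width and would rarely produce a significant Fisher test. All of this stands, and it limits the weight of the point. It does not remove the route for bias, which can be closed cheaply.

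A reader might infer more than the documents support, in five ways:

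- **That chance imbalance in veins is itself a flaw.** It is not. Every trial of 10 per arm has it, and Fisher's test allows for it under the null.
- **That the 38.5% and 60% in section 5.2 measure how much vein choice matters.** They contrast patient populations and say nothing about veins. Section 5.2 names the catheter-to-vein ratio, not basilic, brachial or cephalic site, so vein choice enters through diameter. The contrast should not be used.
- **That the vein is not recorded.** The Surgical Summary may hold it. The scans under 13.7 follow the catheterised vein on a form with a picture of the vein, and section 16.1 would summarise any numeric baseline item collected. The content of 7.3 is not visible. The gap shown is in sequence and planned reporting, not necessarily in data capture.
- **That a difference between arms would be uninterpretable because of insertion factors.** With 10 per arm, imprecision is the larger obstacle.
- **That inserters are less practised with HydroPICC.** Section 8.1 says it is not the site's standard device, but only to explain consent. Inserter training is not described.

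**Conclusion.** The point holds as a matter of sequence. In an unblinded trial the plan allows the device to be known before the vein is assessed and chosen, gives no criterion for moving between veins, and names no insertion factor in its summaries.

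The size of any resulting bias cannot be derived from the documents. The 2 to 24 points is a sensitivity range resting wholly on assumed risks and shares, and it presumes that knowing the device does alter the choice. A false significant result from this source alone is unlikely (at most 0.076 in those scenarios). The exposure lies in the point estimate and in what the larger study takes from it.

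The change of sequence is worth making because it removes the route at a time the schedule already allows. The added tables support it but would not justify an amendment on their own.

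**What to change.** 1. Amend 10.5, 14.1 step 9, 14.2 and the schedule so that the envelope is opened at Visit 2, only after the pre-insertion scan is complete and the intended vein and its diameter are recorded.
2. Add intended vein and vein diameter, by arm, to the section 16.4 baseline summaries.
3. Add a separate descriptive table of insertion details by arm: vein used (with the reason if it differs from the intended vein), catheter-to-vein ratio, number of attempts, inserter and tip position. Draw on the Surgical Summary where it already records these. They arise after assignment, and the ratio depends partly on the device, so they do not belong with baseline data.
4. Leave the primary tests unadjusted; 10 per arm does not support a useful adjusted analysis. If any result is shown by vein, use the intended vein and label it descriptive. Splitting by vein used would condition on a choice the device may have influenced.

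The order of vein preference is left as it is.

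**Cost.** No visit, procedure or subject is added: 20 analysed and 24 enrolled are unchanged. A protocol amendment and a few form fields are needed, both devices must be at hand at insertion, and randomisation at screening is no longer possible. One side benefit is that a subject excluded at the scan would no longer have used an envelope.
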